6.5 Analysis of quality of life variables

Not applicable.

6.6 Analysis of pharmacoeconomic variables

Not applicable.

6.7 Analysis of epidemiological measures and risk-benefit evaluations

Not applicable.

6.8 Analysis of pharmacodynamic variables

For categorical variables, the incidence of subjects by category will be summarized by using frequency counts, percentages and the corresponding 95% confidence interval (CI) when relevant.

Continuous variables will be summarized using: arithmetic mean, SD, minimum, 1st quartile, median, 3rd quartile, maximum, and 95% CI of the mean when relevant.

6.8.1 Primary pharmacodynamic endpoint

The study is designed to demonstrate that a single injection of ACT-246475 enables a large proportion (a target of 85%) of subjects to achieve a clinically meaningful level of inhibition of platelet aggregation (IPA), i.e., PRU < 100 at 30 minutes after study drug injection.

6.8.1.1 Variable

The primary pharmacodynamic (PD) endpoint is the *PD response* that is defined for each subject as a PRU < 100 at 30 min after study drug injection, as measured via VerifyNow[®].

The primary PD variable (PRU_{30m}) is the platelet reactivity as measured by VerifyNow[®] at 30 min after study drug injection [see the table of assessments in the protocol, table 2].

The analysis variable of the PD response is defined as follows for a given subject:

$$\begin{aligned} & \text{IF } PRU_{30m} < 100 \\ & \text{THEN } PD \text{ response} = \text{YES} \\ & \text{ELSE } PD \text{ response} = \text{NO} \end{aligned}$$

PRU time is based on planned time point and not on the actual collection time.

Supportive primary PD endpoint

The following endpoint is not described in the protocol and has been added. The main purpose is to assess the effect of the two study treatment doses, when relaxing the time of a PRU < 100, i.e., considering as a response a PRU < 100 at 15, 30 or 60 min. post injection.

This endpoint is defined as per the following algorithm and will describe the subject's *PD response within the 1st hour*:

*IF minimum of (PRU_{15m}, PRU_{30m}, PRU_{60m}) < 100
THEN PD response within 1st hour = YES
ELSE PD response within 1st hour = NO*

Where PRU_{15m}, PRU_{30m}, and PRU_{60m} refer to PRU measured by VerifyNow® at 15, 30, and 60 minutes after study drug administration.

PRU time is based on planned time point and not on the actual collection time.

6.8.1.2 Analysis

The analyses described in this section consider the primary endpoint, i.e., PD response. Sensitivity analysis of the PD endpoints will be described in Section 6.8.1.3.

Unless stated otherwise, all analyses will be conducted on the mFAS.

Hypotheses and statistical model

The primary objective is to assess IPA 30 min after a single s.c. injection of ACT-246475 in subjects with AMI receiving conventional antithrombotic treatment (e.g., aspirin, oral P2Y₁₂ receptor antagonists, anticoagulants).

To achieve this objective, the testing strategy will be to test the study treatment effect (using the proportion *p* of responders, i.e., achieving PRU < 100 at 30 minutes post-injection) for each of the two doses, considering the following hypotheses:

$$H_{0HD}: p_{HD} \leq 50\% \text{ vs } H_{1HD}: p_{HD} \geq 85\%$$

$$H_{0LD}: p_{LD} \leq 50\% \text{ vs } H_{1LD}: p_{LD} \geq 85\%$$

where LD is the lower ACT-246475 dose (8 mg), and HD the higher ACT-246475 dose (16 mg).

Each of the two null hypotheses will be tested by a two-sided z-test at a significance level (alpha) of 0.025, which is an overall level of 0.05 for the study level and adjusted for multiplicity using Bonferroni method.

Main analysis

The primary statistical analysis will be performed on the mFAS population for each dose level.

It will be based on the study treatment received (which may differ from the assigned one).

The analysis of the primary endpoint will be performed for each of the two doses independently, i.e., considering 2 null hypotheses (proportion of patients achieving a

response is less than or equal to 50%) at 0.025 type I error each [see protocol section 10.3.3.1].

The study will be declared positive for the primary objective, if at least 1 out of the 2 null hypotheses is rejected at 0.025 type I error level.

A one-sided z-test will be computed and the 95% CI of the proportion of responders will be provided.

A summary of response, in terms of number (%) of responding subjects, will be provided.

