### 3.2 Study design rationale

The duration of the treatment period is justified by the primary objective, which is to characterize the onset of IPA after a single s.c. injection of ACT-246475 at two different doses in subjects with AMI.

The choice of the same two doses (i.e., 8 and 16 mg) as in the ongoing ID-076A201 study (see Section 5.1.1 for detailed rationale on dose selection), will provide supportive information for the selection of the dose to be tested in the Phase 3 pivotal study.

The IPA analysis will be performed with the VerifyNow® method. Results from VerifyNow® are well correlated with those obtained with the light transmission aggregometry (LTA) method [Varenhorst 2009, Gremmel 2015]. The VerifyNow® method has been preferred as it is more standardized than the LTA method and it is the method used for primary PD analysis in the ongoing ID-076A201 study in subjects with stable CAD. In addition, the volume of blood required per sample is higher for LTA (6 mL) than for the VerifyNow® method (3 mL). Accordingly, using the VerifyNow®

method will reduce the amount of blood collected for study purposes in a population with acute ischemic event.

The trial is conducted open-label to allow the investigator to adapt the standard AMI treatments to an individual subject's needs (e.g., antiplatelet and anticoagulant treatment). In addition, the primary endpoint being a pharmacological readout (P2Y12 reaction units [PRU] value at 30 min) with no room for data interpretation, the open-label design is fully justified. Because of the limited sample size and the absence of a placebo group, the presentation of the safety data will be purely descriptive.

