##### **10.3.3.1 Hypotheses and statistical model**

The primary objective is to assess IPA 30 min after a single s.c. injection of ACT-246475 in subjects with AMI receiving conventional antithrombotic treatment (e.g., aspirin, oral P2Y12 receptor antagonists, anticoagulants).

In order to achieve this objective, the testing strategy will be to test the treatment effect (using the proportion  $p$  of responders, i.e., achieving PRU < 100) for each of the two treatment arms considering the following hypotheses:

$$H_{0HD}: p_{HD} \leq 50\% \quad \text{vs} \quad H_{1HD}: p_{HD} \geq 85\%$$

$$H_{0LD}: p_{LD} \leq 50\% \quad \text{vs} \quad H_{1LD}: p_{LD} \geq 85\%$$

where LD is the lower ACT-246475 dose (8 mg), and HD the higher ACT-246475 dose (16 mg).

Each of the two null hypotheses will be tested by a two-sided z-test at a significance level (alpha) of 0.025, which is an overall level of 0.05 for the study level and adjusted for multiplicity using Bonferroni method.

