### **10.5 Sample size**

The computation of the sample size was performed using East 6.0 software (version 6.4.0.1, 30 August 2016) from Cytel Inc.

The sample size is based on the study primary objective of assessing IPA 30 min after ACT-246475 administration, as assessed by the proportion of subjects achieving a response (i.e., PRU < 100 at 30 min post study drug administration). The sample size should be sufficient to allow the rejection at least one of the null hypotheses.

The study should include 21 subjects evaluable for the primary PD endpoint in each arm considering:

- an overall two-sided type I error of 0.05, adjusted for multiplicity using the Bonferroni method for each of the 2 null hypotheses (testing each dose at an alpha level of 0.025),
- a power of 90%, and
- the following assumptions for the response rate under the null and alternative hypotheses as reported in the table below.

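### Testing each dose at a fixed 0.025 gives up possible rejections for the second dose that Holm's step-down would allow at the same nominal 0.05; the size of the gain depends on which test the plan means

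*SAP*

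**What the plan says.** SAP 6.8.1.2 and protocol 10.3.3.1 set up one null hypothesis per dose, a responder proportion of at most 50%, with 85% as the alternative. The SAP states: "Each of the two null hypotheses will be tested by a two-sided z-test at a significance level (alpha) of 0.025", and describes this as "which is an overall level of 0.05 for the study level and adjusted for multiplicity using Bonferroni method". Protocol 10.3.3.1 uses the same term, "adjusted for multiplicity using Bonferroni method". Neither document has a step-down, and SAP section 11 on changes to the planned analyses does not add one.

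Success needs one dose only: "The study will be declared positive for the primary objective, if at least 1 out of the 2 null hypotheses is rejected". The sample size follows that aim: "The sample size should be sufficient to allow the rejection at least one of the null hypotheses" (protocol 10.5). It is based on "an overall two-sided type I error of 0.05, adjusted for multiplicity using the Bonferroni method for each of the 2 null hypotheses", 90% power and 21 evaluable subjects per arm.

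Later in the same SAP section, under the main analysis, the test changes sidedness: "A one-sided z-test will be computed and the 95% CI of the proportion of responders will be provided". Protocol 10.3.3.3 and the synopsis also say one-sided.

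On the use of the two doses, protocol 3.2 says that testing the same doses as in the stable coronary disease study "will provide supportive information for the selection of the dose to be tested in the Phase 3 pivotal study".

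**The concern.** Bonferroni holds each dose to 0.025 whatever happens on the other. Holm starts with the same 0.025 test on the smaller p-value. If that rejects, it tests the larger p-value at 0.05. It needs no assumption that Bonferroni does not need, rejects everything Bonferroni rejects, and keeps the nominal family-wise level at 0.05. With two hypotheses, the fixed split has no offsetting statistical advantage.

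At stake is the formal conclusion on the second dose once the first has succeeded. With 16/21 responders on one dose and 15/21 on the other, the two-sided plan rejects the first null and not the second, whereas Holm on the same z-test rejects both. The plan gives no probability of rejecting both nulls, so the reader cannot see what the choice of procedure costs.

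**Working it through.** **Inputs.** 21 evaluable per arm, 50% under the null, 85% under the alternative, 0.025 per dose and 90% power (protocol 10.5 and Table 4; SAP 6.8.1.2). The arms contain different subjects and are treated as independent.

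**1. The plan's sample size.** For a one-sample z-test with the null variance, n = [(z_α √(p0 q0) + z_β √(p1 q1)) / (p1 − p0)]².

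- Two-sided 0.025: [(2.241 × 0.5 + 1.282 × 0.357) / 0.35]² = 20.3, rounded up to 21. This matches the plan; power at 21 by the same approximation is 91.2%.
- One-sided 0.025: [(1.960 × 0.5 + 1.282 × 0.357) / 0.35]² = 16.9, rounded up to 17. This does not match.

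Of these two readings, only the two-sided one gives 21.

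**2. Cut-offs at n = 21.** z = (x − 10.5)/√5.25 gives 1.528, 1.964 and 2.400 for x = 14, 15 and 16. The exact upper tail at 50% is 0.0392 for 15 or more, 0.0133 for 16 or more and 0.0036 for 17 or more.

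- Two-sided z, 0.025 then 0.05: critical values 2.241 and 1.960, so 16 then 15.
- One-sided z, 0.025 then 0.05: critical values 1.960 and 1.645, so 15 then 15.
- Exact one-sided, 0.025 then 0.05: 16 then 15.
- Exact one-sided, 0.0125 then 0.025: 17 then 16.

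**3. Probability of rejecting both, true response 85% on each dose.** Exact power is 0.9713 for 15 or more, 0.9173 for 16 or more and 0.8025 for 17 or more. Let P1 and P2 be the power at the first-step and second-step cut-offs. Then:

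- Bonferroni, both = P1²
- Holm, both = P2² − (P2 − P1)²
- At least one (either method) = 1 − (1 − P1)²

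| Test | Cut-offs | Both, Bonferroni | Both, Holm | At least one |
|---|---|---|---|---|
| Two-sided z, 0.025 then 0.05 | 16, 15 | 84.1% | 94.0% | 99.3% |
| Exact one-sided, 0.025 then 0.05 | 16, 15 | 84.1% | 94.0% | 99.3% |
| Exact one-sided, 0.0125 then 0.025 | 17, 16 | 64.4% | 82.8% | 96.1% |
| One-sided z, 0.025 then 0.05 | 15, 15 | 94.3% | 94.3% | 99.9% |

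For the first row: 0.9173² = 0.841, and 0.9713² − (0.9713 − 0.9173)² = 0.940.

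**4. Lower true rates, cut-offs 16 then 15.** With 80% on one dose and 85% on the other, 70.6% becomes 85.9%. With 80% on both, 59.2% becomes 78.0%.

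**5. Power per dose under Holm, cut-offs 16 then 15.** P1 + (P2 − P1) × P1 = 0.9173 + 0.0540 × 0.9173 = 0.967. As a check, the probabilities of at least one and of both must add up to twice the per-dose power: 0.993 + 0.940 = 1.933, against 2 × 0.967 = 1.934, equal apart from rounding. The 91.7% belongs to the first-step test alone.

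**6. Exact error in the efficacy direction, cut-offs 16 then 15.** With both nulls true (50%), it is 1 − (1 − 0.0133)² = 0.026 for either method. With one null true and the other dose at 85%, it is 0.013 for Bonferroni and 0.0133 + (0.0392 − 0.0133) × 0.9173 = 0.037 for Holm. The Holm figure cannot exceed 0.039. If the one-sided z-test is used as written, with cut-off 15 for both doses, the error with both nulls true is 1 − (1 − 0.0392)² = 0.077, with or without Holm.

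**The case against.** The strongest case against is that Bonferroni is valid and prespecified, the study is exploratory, and the declared criterion is one dose. Rejecting both nulls is neither an objective nor the basis of the sample size, and responder proportions with 95% intervals are reported for each dose in any case. All of this stands, and it limits the point to an improvement in efficiency.

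Three stronger readings are tempting and are not supported.

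- A reader might infer that dose selection depends on whether both doses beat 50%. Protocol 3.2 calls the information supportive, and 4.2 says the choice will use these results together with those of ID-076A201. No rule links the choice to rejecting both nulls.
- A reader might take the gain of about 10 points as unconditional. If the one-sided z-test at 0.025 is the operative one, Holm gains nothing at exactly 21 per arm. This comes from discreteness: with 20 or 22 evaluable in an arm, Holm lowers the one-sided cut-off by one (15 to 14, or 16 to 15).
- A reader might infer that Holm leaves the actual error untouched, or that 15/21 fails under Bonferroni for no statistical reason. The nominal level is the same, but under the two-sided z-test 15/21 passes only narrowly (1.964 against 1.960). Its exact one-sided p-value is 0.039, and its exact (Clopper-Pearson) 95% interval starts at 47.8%. The false efficacy rejection of 0.037 to 0.039 under Holm is below 0.05 but above 0.025, the upper-tail share of a two-sided 0.05. The z approximation causes this, not Holm, and it is a reason to prefer an exact test.

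**Conclusion.** The point holds as an efficiency gain for the second dose. On none of the four tests compared does Holm do worse than the planned Bonferroni split, and it leaves the probability of declared success where it was (99.3% under the two-sided z-test). For rejecting both nulls, the gain is 9.9 points (84.1% to 94.0%) under the two-sided z-test, the reading that gives the planned 21 per arm, or under an exact one-sided 0.025 test. It is 18.4 points (64.4% to 82.8%) under the exact test at one-sided 0.0125 then 0.025, and zero under the one-sided z-test.

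These figures assume exactly 21 evaluable subjects per arm, independent arms and a true response of 85% at both doses. The unresolved sidedness decides which figure applies, so it has to be settled first.

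**What to change.** 1. Choose one-sided or two-sided and state it consistently in protocol 10.3.3.1 and 10.3.3.3, the synopsis and SAP 6.8.1.2. Preferably name an exact binomial test, because the z-test's exact upper-tail size at 15/21 is 0.039.
2. Replace Bonferroni with Holm: test the smaller p-value at 0.025 and, if it is rejected, the larger at 0.05, both on the chosen sidedness. Keep the success rule as it is. Align protocol 10.3.1 and 10.5, which also carry the 0.025 per-dose level.
3. If power is restated for cut-offs of 16/21 then 15/21, give 91.7% per dose for the first-step test, 96.7% per dose under Holm, 99.3% for at least one dose and 94.0% for both, all at a true 85%.

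The cost is a short protocol amendment and a SAP revision, made before results are seen. Holm needs no extra patients. The choice of test can carry a cost of its own: an exact test at one-sided 0.0125 has first-step power of 80.3% per dose at n = 21, below the planned 90%. That follows from the test and its level, not from Holm, and should be weighed in step 1.

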#### 7.1.1 Screening/re-screening

Screening starts when the subject has provided informed consent. The date on which the first screening assessment is performed corresponds to the date of the study visit.

It is the responsibility of the investigator/delegate to obtain written informed consent from each subject participating in this study after adequate face-to-face explanation of the objectives, methods, and potential hazards of the study. The subjects who will be included in the study are considered as vulnerable and a specific consenting process is detailed in Section [1.4.3](#).

Subjects who have provided informed consent will be allocated a 7-digit subject identification number which will consist of: firsts 4 digits corresponding to the site identification number and lasts 3 digits corresponding to the sequential order of recruitment of the subjects from the site.

Subjects who have provided informed consent when the enrollment target has been met may still be randomized.

Re-screening is not permitted in this study.

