#### **10.3.3 Analysis of the pharmacodynamic variables**

All analyses of PD variables will be performed using the mFAS as primary analysis set, and based on the actually administered treatment, which may differ from the one assigned through the randomization process.

The study is designed to demonstrate that ACT-246475 enables a large proportion (a target of 85%) of the enrolled subjects to achieve a clinically meaningful level of IPA, i.e., PRU < 100.

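### The primary test is specified as both two-sided and one-sided at 0.025 per dose, so 15 responders out of 21 is a success under one sentence and a failure under the other

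*SAP*

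**What the plan says.** SAP section 6.8.1.2 describes the primary test twice.

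- Under Hypotheses and statistical model: "Each of the two null hypotheses will be tested by a two-sided z-test at a significance level (alpha) of 0.025". The sentence goes on to describe this as a Bonferroni split of an overall 0.05.
- Under Main analysis, the study is declared positive "if at least 1 out of the 2 null hypotheses is rejected at 0.025 type I error level". The next sentence reads: "A one-sided z-test will be computed and the 95% CI of the proportion of responders will be provided".

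Protocol section 10.3.3.1 has the two-sided sentence and section 10.3.3.3 the one-sided one. The protocol synopsis, reproduced as SAP Appendix A, repeats the one-sided wording beside a two-sided sample-size basis. Protocol section 10.5 derives 21 evaluable subjects per arm from "an overall two-sided type I error of 0.05, adjusted for multiplicity using the Bonferroni method for each of the 2 null hypotheses", with 90% power and response rates of 50% and 85%.

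SAP section 11, which lists changes and clarifications, does not mention sidedness. No sentence sets the one-sided test at 0.0125, which would make the two descriptions equivalent. Neither document says whether z uses the null or the sample variance, or whether a continuity correction applies.

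**The concern.** This rule decides whether the study is positive, and two analysts following the same SAP section could reach opposite verdicts from the same counts. The trial is open-label, so nothing in the plan prevents the ambiguity from being settled once the counts are known. One rejected null hypothesis is enough for a positive study, so the verdict turns on the better arm.

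The ambiguity also spreads. The main analysis is reused for response within the first hour (SAP 6.8.1.3), for the subgroups (6.8.1.4) and for PRU status at 60 minutes (6.8.2.2).

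**Working it through.** **Inputs.** Null rate 50% and per-dose level 0.025 (SAP 6.8.1.2); alternative 85% (Protocol 10.3.3 and 10.5); power 90% and n = 21 per arm (Protocol 10.5). Critical z is 1.960 for one-sided 0.025 and 2.241 for two-sided 0.025; z for 90% power is 1.2816.

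**Reproducing the sample size.** n = ((z·√(0.5·0.5) + 1.2816·√(0.85·0.15)) / 0.35)²

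- z = 2.241 gives 20.34, so 21, which is the stated figure.
- z = 1.960 gives 16.87, so 17.

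With the same formula, one-sided 0.05 gives 14 and two-sided 0.0125 gives 24. The planned size therefore rests on the two-sided reading.

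**Decision at 21 per arm.** With the null variance, z = (x/21 − 0.5)/√(0.25/21).

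| Responders | z, null variance | z, sample variance | z, continuity-corrected | Exact tail at 50% |
|---|---|---|---|---|
| 14 | 1.528 | 1.620 | 1.309 | 0.0946 |
| 15 | 1.964 | 2.174 | 1.746 | 0.0392 |
| 16 | 2.400 | 2.818 | 2.182 | 0.0133 |
| 17 | 2.837 | 3.612 | 2.619 | 0.0036 |

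At 15 the null-variance p-value is 0.0248 one-sided and 0.0495 two-sided. One-sided/two-sided cutoffs are 15/16 with either variance and 16/17 with the continuity correction. Each version of z leaves one count on which the two sentences disagree.

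**Probability that the study verdict differs.** With the uncorrected null-variance z, this happens when the better arm has exactly 15 responders. For independent arms with the same true rate p, the probability is F(15)² − F(14)², where F is the binomial(21, p) distribution function. At p = 0.65 it is 0.799² − 0.643² = 0.225.

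| True rate in both arms | 50% | 60% | 65% | 70% | 75% | 85% |
|---|---|---|---|---|---|---|
| Verdict differs | 5.0% | 17.8% | 22.5% | 20.4% | 12.2% | 0.6% |

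**Other arm sizes.** Final arm sizes may not be exactly 21. Non-evaluable subjects are replaced, subjects are analysed by dose received, and Protocol 7.1.1 says: "Subjects who have provided informed consent when the enrollment target has been met may still be randomized". With the null variance, the one-sided/two-sided cutoffs at 19 to 25 per arm are 14/15, 15/16, 15/16, 16/17, 17/17, 17/18 and 18/19, so they differ at six of the seven sizes. With the sample variance they differ only at 21 and 23. With the continuity correction they differ at 20, 21, 23 and 25.

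**The interval.** A two-sided 95% CI corresponds to one-sided 0.025. A two-sided 0.025 test needs a 97.5% CI. The Wilson limits, which match the null-variance z, show this at 15/21: the 95% lower limit is 50.04%, just above the null, and the 97.5% lower limit is 47.0%.

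**A separate point: the normal approximation.** This is not caused by the sidedness conflict. With a true rate of 50% in both arms, a cutoff of 15 at 21 per arm has exact error 3.92% per dose and 1 − (1 − 0.0392)² = 7.7% overall. A cutoff of 16 has 1.33% per dose and 2.6% overall. Power at 85% is 97.1% and 91.7% respectively.

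**The case against.** The strongest reply is that the text can be read as two-sided. The one-sided sentence carries no alpha of its own, the Main analysis part refers back to Protocol 10.3.3.1, where the two-sided clause sits, and 21 per arm reproduces only on that basis. The one-sided test could then be just the directional form of the two-sided one. This makes a two-sided intention plausible, but it does not settle the rule. The sentence naming the test to be computed says one-sided, the only per-dose level given is 0.025, and the 95% CI fits that reading.

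Three qualifications stand.

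- The count of 15 assumes no continuity correction; with one, the disputed count is 16. The six-of-seven result across arm sizes holds only for the null variance.
- At the design rate of 85% the flip is rare. True rates of 65% to 70% are an assumption, although Protocol 1.3 and 4.2 do allow that acute infarction may impair subcutaneous uptake.
- The study is exploratory, and dose selection also draws on ID-076A201. It nevertheless has a formal success declaration.

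The choice of an exact test and of an interval method is an improvement, and the case for a correction does not depend on it.

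**Conclusion.** The concern holds. Both sentences are in current text, and they give different success cutoffs at the planned 21 per arm under each of the three forms of z checked. With the uncorrected z, 15 of 21 is the disputed result. The study verdict then differs with probability 0.6% if both doses truly reach 85%, and 20% to 22% at 65% to 70%, assuming independent arms of 21 with equal true rates. The documents point both ways: the sample size supports two-sided 0.025, and the 95% CI supports one-sided 0.025. Naming one test and one alpha is a must-fix. The exact test and the interval method are should-fix.

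**What to change.** **Required.** State one primary test and one per-dose alpha in SAP 6.8.1.2 and remove the conflicting wording. The one-sided sentence also contains the CI specification, so that must be kept and matched to the chosen test. Record the clarification in SAP 11.3, saying that it supersedes the corresponding protocol and synopsis wording.

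**Preferred.** Use an exact binomial test at one-sided 0.025 per dose, with the cutoff computed from the number evaluable in each arm. At 21 the cutoff is 16. Over 19 to 25 per arm the overall error stays between 1.7% and 4.3%. Report the Clopper-Pearson 95% CI, which agrees with this test (lower limit 47.8% at 15/21 and 52.8% at 16/21). Because this replaces the planned z-test, it should be listed as a change in SAP 11.1.

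**Alternative.** Keep the two-sided 0.025 z-test behind the sample size and state the variance and whether a continuity correction applies. With the null variance and no correction, the cutoff at 21 is also 16, and the matching interval is the Wilson 97.5% CI (lower limit 51.7% at 16/21). A Clopper-Pearson 97.5% CI would not match, because its lower limit at 16/21 is 49.7%. A continuity correction would raise the cutoff to 17 and lower power at 85% to 80.3%.

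**Cost.** Wording only, with no extra patients. At 21 per arm, the exact test and the uncorrected two-sided z-test both keep the stated 90% power (91.7%), and 15 of 21 no longer counts as success. The two options are not identical at other sizes. At 20 per arm the exact test needs 15 (power 93.3%) and the null-variance two-sided z-test needs 16 (83.0%); at 25 they need 18 and 19. At 19 both need 15, with power 85.6%.

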#### ***10.3.3.3 Main analysis***

The primary statistical analysis will be performed on the mFAS population for each dose level.

It will consider the treatment actually received (which may differ from the assigned one).

The analysis of the primary endpoint will be performed for each of the two doses independently, i.e., considering 2 null hypotheses (proportion of patients achieving a response is less than or equal to 50%) at 0.025 type I error each [see Section 10.3.3.1].

The study will be declared positive with regard to the primary objective, if at least 1 of the 2 null hypotheses is rejected at 0.025 type I error level.

A one-sided z-test will be computed and the 95% CI of the proportion of responders will be provided.

Summary of response, in terms of number (%) of responding subjects, will be provided.

IPA as measured by VerifyNow® will also be summarized as a continuous variable.

Those summaries will also be provided considering the available PD assessment time points (15 min and 60 min post-dose).

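### The primary z-test is given as both one-sided and two-sided at 0.025; on the one-sided reading, 15/21 counts as success with an exact p of 0.039, so the stated error rates are not held at 21 per arm

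*SAP*

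**What the plan says.** The primary endpoint is a responder count per dose (PRU below 100 at 30 minutes). It is tested in each arm against a null response rate of at most 50%, with a target of 85%.

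The level is stated consistently. The SAP tests each null ("response is less than or equal to 50%) at 0.025 type I error each"), and under protocol 10.3.3.3 the study is positive "if at least 1 of the 2 null hypotheses is rejected at 0.025 type I error level". Protocol 10.5 plans for "an overall two-sided type I error of 0.05, adjusted for multiplicity using the Bonferroni method for each of the 2 null hypotheses", which it explains as "testing each dose at an alpha level of 0.025", with 90% power and 21 evaluable subjects per arm.

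The test is not stated consistently. Within SAP 6.8.1.2:

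- Under the hypotheses: "Each of the two null hypotheses will be tested by a two-sided z-test at a significance level (alpha) of 0.025".
- Under the main analysis: "A one-sided z-test will be computed and the 95% CI of the proportion of responders will be provided".

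Protocol 10.3.3.1 and 10.3.3.3 contain the same pair, and the synopsis carries the one-sided sentence. Neither document states the variance used in the z-statistic, whether a continuity correction applies, or how the 95% CI is computed.

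Arm size is not fixed at 21. Enrolment is approximately 42, subjects without the 30-minute value are replaced, groups follow the dose received, and protocol 7.1.1 adds "Subjects who have provided informed consent when the enrollment target has been met may still be randomized".

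**The concern.** A responder count out of about 21 is discrete, and a z-test refers it to a continuous distribution. The actual error rate then depends on where the z cut-off falls between two counts and can lie well above or below the nominal level. The plan makes a formal commitment: 0.025 per dose, 0.05 overall, and a declared positive study if either dose succeeds. If the operative rule is the one-sided sentence, the study can be declared positive on a count whose exact p-value misses the stated threshold. The two sentences also give different verdicts on the same result, 15/21, so a programmer and a reader could disagree about whether the trial succeeded. According to protocol 3.2 and 4.2, the results help to select the Phase 3 dose.

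**Working it through.** **Inputs.** Null rate 0.50, target rate 0.85, power 90%, 21 evaluable per arm (protocol 10.5). Level 0.025 per dose, success if either null is rejected (protocol 10.3.3.3, SAP 6.8.1.2). The arms contain different subjects, so they are independent. The z-statistic uses the null standard error without continuity correction, which is an assumption because the documents are silent.

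**1. Which version reproduces the planned 21?** n = [(z_α·√(p0·q0) + z_β·√(p1·q1)) / (p1 − p0)]², with √(0.5·0.5) = 0.5, √(0.85·0.15) = 0.3571 and z_β = 1.2816.

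- Two-sided 0.025 (z = 2.2414): [(2.2414·0.5 + 1.2816·0.3571)/0.35]² = 20.3, rounded up to 21. This reproduces the plan.
- One-sided 0.025 (z = 1.960): 16.9, rounded up to 17. This does not.

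**2. Cut-off at n = 21.** z = (x/21 − 0.5)/√(0.25/21).

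- x = 15: z = 1.964. This exceeds 1.960, so the one-sided test rejects. It is below 2.241 (two-sided p = 0.0495), so the two-sided test does not.
- x = 16: z = 2.400. Both reject.

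A Wald standard error gives z = 2.17 at x = 15, hence the same two verdicts on 15/21.

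**3. Exact error at n = 21 when the true rate is 50%.**

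- One-sided rule (15 or more): P(X ≥ 15) = 0.0392. Study-wise: 1 − (1 − 0.0392)² = 0.0768.
- Two-sided rule (16 or more in the upper tail): P(X ≥ 16) = 0.0133. Study-wise false claim of benefit: 1 − (1 − 0.0133)² = 0.026. Counting both tails gives 2 × 0.0133 = 0.0266 per dose, marginally above 0.025.

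**4. Other arm sizes.** Each cell gives the upper cut-off and the exact upper-tail error; power is at a true rate of 85%.

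| n per arm | One-sided z, 0.025 | Two-sided z, 0.025 | Exact one-sided, 0.025 | Power of exact test |
|---|---|---|---|---|
| 18 | 14, 0.0154 | 14, 0.0154 | 14, 0.0154 | 87.9% |
| 19 | 14, 0.0318 | 15, 0.0096 | 15, 0.0096 | 85.6% |
| 20 | 15, 0.0207 | 16, 0.0059 | 15, 0.0207 | 93.3% |
| 21 | 15, 0.0392 | 16, 0.0133 | 16, 0.0133 | 91.7% |
| 22 | 16, 0.0262 | 17, 0.0085 | 17, 0.0085 | 90.0% |
| 23 | 17, 0.0173 | 17, 0.0173 | 17, 0.0173 | 95.4% |
| 24 | 17, 0.0320 | 18, 0.0113 | 18, 0.0113 | 94.3% |

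The one-sided z-test moves irregularly around 0.025: above it at 19, 21, 22 and 24, below it at 18, 20 and 23. The planned 21 is the worst of these sizes.

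**5. Agreement with the confidence interval.** The Clopper-Pearson 95% CI for 15/21 is 47.8% to 88.7%, which includes 50%. If the SAP's unnamed CI method is the exact one, the report could declare success on 15/21 next to an interval that contains the null value.

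**The case against.** The strongest reply is that 7.7% is not a property of the plan as a whole. The hypotheses text specifies a two-sided test, the sample-size section speaks of a two-sided overall error, and only that version yields 21 per arm. Under it 15/21 fails and the cut-off is already 16/21. From 17 to 27 subjects per arm its upper-tail error never exceeds 0.0173 per dose, or 1 − (1 − 0.0173)² = 3.4% for the study. This stands. A reader might infer that the study-wise error simply is 7.7%; the documents support that only on the one-sided branch.

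A reader might also infer that settling the sidedness would leave the problem in place, because the two-sided z-test has an exact two-tailed size of 0.0266 at n = 21 and 0.0347 at n = 23. Those figures include the lower tail. The nulls are p ≤ 50%, so too few responders cannot produce a false claim of benefit. Settling on the two-sided rule does bring false success below 5%; what remains is a small departure from the nominal two-tailed level.

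Three further limits are fair:

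- The 7.7% is a worst case, with both true rates exactly 50% and exactly 21 in each arm. At a true 45% in both arms the one-sided rule gives 2.6%. Type I error for a null of the form p ≤ 50% is nevertheless judged at its maximum, so the figure is the right one to compare with the promise.
- No continuity correction is an assumption. With one, 15/21 gives z = 1.75 and fails.
- The study is labelled exploratory, and responder counts with a CI are reported per dose, so a borderline 15/21 would be visible.

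Against this, the one-sided sentence stands under the main analysis in both documents, beside the success rule, and is the one most likely to be programmed.

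**Conclusion.** The concern holds conditionally. The primary test is described in two incompatible ways. If the one-sided main-analysis sentence is applied without continuity correction at 21 per arm, 15/21 counts as success with an exact p of 0.0392. The error is then 0.039 per dose and up to 7.7% for the study, against the stated 0.025 and 0.05. At other arm sizes the excess comes and goes. Under the two-sided z-test, which matches the sample size, false-success error is 0.0133 per dose and 2.6% for the study, and only the two-tailed size is marginally above nominal. At n = 21 the dispute concerns a single count, 15/21. This should be fixed, but the sample size and the design can stay as they are.

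**What to change.** Reconcile the sidedness in protocol 10.3.3.1, 10.3.3.3, 10.5 and the synopsis, and in SAP 6.8.1.2. Replace the z-test with an exact binomial test of p ≤ 50% at one-sided 0.025 per dose. State the rule at n = 21 (16 or more responders), and state that the cut-off is recomputed from the exact distribution if an arm differs from 21. Name the matching Clopper-Pearson 95% CI. Its lower limit exceeds 50% exactly when the one-sided 0.025 test rejects, so test and interval cannot disagree.

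At n = 21 the size is 0.0133 per dose and 2.6% for the study, with 91.7% power at 85%, so the stated 90% is kept without extra subjects. At any arm size the study-wise error is at most 1 − 0.975² = 4.9%.

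The cost is wording and one procedure option. 15/21 no longer counts as success, and power is 91.7% rather than the 97.1% that the one-sided z-test gives with its inflated error. If an arm ends at 18 or 19, power falls below 90% (87.9% and 85.6%). The overall error in 10.5 would have to be described as one-sided. If the sponsor instead keeps an exact test at the two-sided 0.025 level (0.0125 in the upper tail), the cut-off becomes 17/21, size 0.0036, and the stated power must be restated as 80%.
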